## **Methods**

The project will be carried out at the Center for Clinical Research and Prevention (CCRP), formerly known as *Research Center for Prevention and Health (RCPH)*, '*The Population Surveys in Glostrup*', which has more than 50 years of experience in conducting population surveys. Data collection is scheduled to be completed during the period 1 January 2018 to August 2018 and it is expected that 450 children and adults divided into 120 families will participate.

At baseline and endpoint participants will be examined about salt intake (24 hr urine collection, 7-day dietary record), salt preferences and salt sensitivity, blood pressure, anthropometry, blood lipids, sugar metabolism and hormones. The intervention will last 14+ weeks.

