Official title of the study: Salt Reduction InterVENTion: Examination of the metabolic, behavioral and health consequences of reducing salt intake. A randomized controlled trial in a real life setting.

NCT number: Not yet assigned

Date of the document: November 30, 2018

Statistical analysis plan STRIVE

Statistical Analysis Plan STRIVE

We are currently writing up a more in-depth plan of the statistical analysis plan, which will be uploaded when ready.

Aim: The Salt Reduction InterVENTion (STRIVE) aims to investigate the metabolic, behavioral and health effects of 14+ weeks of gradually salt reduced bread alone or in combination with dietary counselling compared to families receiving standard bread.

Design: Randomised, controlled trial with three parallel arms

Methods: Eligible families will be randomly allocated into three groups to investigate the effect of different salt reduction strategies: **A:** salt reduced bread; **A+B:** Salt reduced bread and dietary counseling; **C:** Bread with standard salt content. Participants will be instructed to replace their usual consumption of bread by bread products provided in the study. The primary outcome is changes in sodium intake measured by 24 hr urine excretion. Secondary outcomes are change in potassium and Sodium/ Potassium ratio, blood pressure, blood lipids, salt-taste sensitivity and renin, aldosterone and sympathetic nervous response. Participants will be examined before and by the end of the intervention. The flow of the trial is shown in figure. 1.

Sample size

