The average daily intake of bread in Denmark is 139 grams (123 gram for children. One of the inclusion criteria is a daily intake of bread of 175 gram among adults. The average salt content of bread in Denmark is 1.3 gram/100-gram bread. Thus, the average daily intake of salt from bread among the participants is estimated to be approximately 2.3 gram. The expected reduction in salt intake due to the salt-reduced-bread intervention (average reduction of 55%) is 1.25 gram per day. The expected salt reduction in the intervention group with the combined intervention is on average 3 gram (based on the current average daily salt intake and the target for the intervention). The statistical power calculations were based on data from a population-based study at Center for Clinical Research and Prevention, DK (CCRP) showing an average daily intake of salt of 8.3 gram (SD 2.2). The analyses were done to fit the cluster-randomized design and showed that if the true difference in the intervention and control means after intervention is 1.2 gram per day we will need to include 50 subjects in each of the three groups to be able to reject the null hypothesis at a 5% level and with probability (power) 0.8. The intra-class correlation within families was assumed to be 0.33 and the average family was assumed to consist of four members. With an expected difference in salt intake of 1.2 gram/day we will expect to see clinical relevant differences in blood pressure, blood lipids, renin, aldosterone and albuminuria.

Randomization, allocation and concealment

Once included, baseline assessments will be conducted before the families will be randomized (1:1:1) to three groups (salt reduced bread, salt reduced bread and dietary counseling, standard bread no dietary counseling), using simple randomization.

A *data manager*, who has no other involvement in the trial than producing the data application will produce a computer-generated sequence of random group assignments (allocation sequence). *Participants* will be blinded to the treatment they receive. Bread will be coded by a red or blue label, and families collect

bread according to the color of their group. The color code will be known by two *bakers* responsible for baking the bread but blinded to the rest of the *bakery staff*, including those handing out the bread to the

[figure not shown]

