Table 1 lists the outcome variables and assessment tools. The *primary study outcome* is the change in 24-h sodium (mean of 3 collections in adults, 1 collection in children). *Secondary outcomes* are change in potassium and Sodium/ Potassium ratio, blood pressure, blood lipids, salt-taste sensitivity and renin, aldosterone and sympathetic nervous response.

Baseline data will be presented as means (std) or medians (with range) for continuous data depending on the distribution of the variable. Categorical variables will be presented as frequencies and percentages.

Estimation of treatment effect for the primary outcome will be calculated using an “intention to treat” analysis, including all randomized participants regardless of the adherence to the intervention and dropouts. To create a full analysis data set, missing data for the primary outcome will be imputed using multiple imputation with 100 samples. A linear mixed model with change in sodium excretion as outcome variable, treatment group and baseline sodium excretion as fixed effects, and family ID as random effect.

The estimates or the size of treatment effects will be presented along with 95% confidence intervals and actual p-values. Levels of significance will be set at 0.05. The primary analysis will be unadjusted.

To account for differences in the adherence to the bread intervention, a per-protocol linear mixed model analysis will be undertaken following the principles outlined above.

Linear mixed models will also be applied to the analyses of the secondary outcomes.

Further analyses will be described in the statistical analysis plan, which we are currently writing up.

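### The SAP's 50 subjects per group does not follow from its own inputs, which give about 105 per group once family clustering is counted

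*SAP*

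**What the plan says.** The SAP's Sample size section takes an SD of 2.2 g/day from a population study (mean intake 8.3 g), a 5% level and power 0.8. It sets the target effect with "if the true difference in the intervention and control means after intervention is 1.2 gram per day". On clustering it says "The analyses were done to fit the cluster-randomized design" and "The intra-class correlation within families was assumed to be 0.33 and the average family was assumed to consist of four members". It concludes that "we will need to include 50 subjects in each of the three groups". The same section expects a reduction of 1.25 g/day from bread alone and 3 g/day from the combined intervention. It states no sidedness, no baseline-to-endpoint correlation and no dropout allowance.

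The SAP's Statistical analysis section plans a linear mixed model for change in sodium excretion with "treatment group and baseline sodium excretion as fixed effects, and family ID as random effect". In the Protocol's Methods section, "it is expected that 450 children and adults divided into 120 families will participate". Neither document connects that number to 50 per group.

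**The concern.** The section gives every input of a standard calculation except sidedness, so the result can be checked, and 50 is less than half of what those inputs produce. It is even slightly below the figure for individual randomization, although the text says clustering was taken into account.

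The contrast at stake is the smaller effect, close to what is expected from bread alone versus control. A reader judging a null result there would take 50 per group as enough for 80% power. On the SAP's own inputs it gives roughly an even chance of detecting 1.2 g/day. Because the section has no dropout allowance and no link to the expected 450 people, a reader also cannot tell what number the trial needs to retain.

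**Working it through.** **Inputs.** From the SAP, Sample size: difference 1.2 g/day, SD 2.2 g, level 5%, power 0.8, ICC 0.33, average family size 4, stated n = 50 per group. From the Protocol, Methods: 450 people in 120 families, that is 150 people and 40 families per group, 3.75 per family. Assumptions made here: a two-sided test (the SAP reports 95% confidence intervals), equal family sizes and no loss.

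**Attempt to reproduce 50.**

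- Individual randomization: n₀ = 2(1.960 + 0.842)² × 2.2² / 1.2² = 52.8, so 53 per group.
- Design effect: 1 + (4 − 1) × 0.33 = 1.99.
- Clustered: 52.76 × 1.99 = 105.0 per group.
- ICC that would give 50: (50/52.76 − 1)/3 = −0.02, so none at or above zero.
- SD that would give 50 at design effect 1.99: 2.2 × √(50/105.0) = 1.52 g.

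**Other readings.**

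| Reading | Unclustered | × 1.99 | ICC needed for 50 |
|---|---|---|---|
| Two-sided, 1.2 g | 52.8 | 105.0 | none ≥ 0 |
| One-sided, 1.2 g | 41.6 | 82.7 | 0.07 |
| Two-sided, 1.25 g | 48.6 | 96.8 | 0.01 |
| One-sided, 1.25 g | 38.3 | 76.2 | 0.10 |
| Two-sided, 3 g | 8.4 | 16.8 | not relevant |

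None gives 50 at the stated ICC. The nearest match is 1.25 g with no clustering: 49, or 50 with a t-based calculation. This suggests that the design effect was left out, but that is an inference.

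**What 50 per group delivers, in families of four.**

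- Noncentrality: 1.2 / (2.2 × √(2 × 1.99/50)) = 1.933. Power is 0.489 (normal), or 0.457 with 23 family-level degrees of freedom. Ignoring clustering it would be 0.78.
- Difference detectable with 80% power: 2.802 × 2.2 × √(2 × 1.99/50) = 1.74 g/day.
- For 3 g/day: noncentrality 4.83, power 0.998. That contrast is unaffected.

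**Baseline adjustment.** If adjustment multiplies the residual variance by 1 − r², the correlation that brings n to 50 is r = √(1 − 50/n). The residual ICCs of 0.20 and 0.10, and all values of r, are assumptions.

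| Residual ICC | n without adjustment | r needed for 50 | Power at 50 for r = 0.3, 0.5, 0.7 |
|---|---|---|---|
| 0.33 | 105.0 | 0.72 | 0.53, 0.61, 0.77 |
| 0.20 | 84.4 | 0.64 | 0.62, 0.70, 0.86 |
| 0.10 | 68.6 | 0.52 | not tabulated |

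**Whole families.** 27 families (108 people) per group give power 0.811 (normal) or 0.796 (t, 52 df). 28 families (112 people) give 0.825 or 0.811 (t, 54 df).

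**Expected recruitment.** With 150 people in 40 families per group, the design effect is 1 + 2.75 × 0.33 = 1.9075 and power is 0.928 (normal) or 0.922 (t, 78 df).

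**Loss, counting lost people as contributing no information.** With an assumed 30% loss (105 left per group), power is 0.80 if whole families of four are lost. It is 0.89 if individuals are lost evenly across the 40 families (design effect 1 + (105/40 − 1) × 0.33 = 1.536). Power falls to 80% at about 30% loss of whole families, about 50% random loss of individuals, or about 58% perfectly even loss of individuals. Fifty people spread evenly over 40 families would give 0.75.

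**The case against.** The strongest defence is that the calculation used a variance reduction the text does not report. The primary model adjusts for baseline sodium, adults contribute a three-day mean, and the SD came from a data set that could have supplied a correlation. The documents cannot rule this out, and a correlation of 0.52 to 0.72, depending on the residual ICC, would be enough. But the section describes a difference in post-intervention means with the population SD and names no correlation. If one was used, the text omits the assumption that drives its result.

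The second objection is about consequence. Nothing in the documents uses 50 as a recruitment target or minimum analysed number, the expected 150 per group exceeds 105, and the analysis model does not depend on this sentence. All of that stands, and it limits the point to an error in the justification.

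Third, 105 rests on equal families. The SAP gives four as an average, and the Protocol puts separated parents' households in one allocation, so cluster sizes will vary. With an assumed coefficient of variation of 0.3 to 0.5, the design effect 1 + [(1 + CV²) × 4 − 1] × 0.33 is 2.11 to 2.32, giving about 111 to 122 per group. At 150 per group with mean size 3.75, power becomes about 0.91 to 0.89. This is fair, and it moves the requirement further from 50.

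Finally, the loss patterns are illustrations, and the most even one is unlikely among families of at least two. The SAP does not label 1.2 g as the bread-alone effect; that reading rests on the 1.25 g it expects for that arm.

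**Conclusion.** The concern holds. On the SAP's stated inputs the requirement is about 105 per group, not 50, and at 50 in families of four the power for 1.2 g/day is about 0.49 rather than 0.80. This rests on a two-sided 5% level, equal families of four, no loss and no gain from baseline adjustment. One-sided testing or 1.25 g/day does not rescue the figure, and unequal families raise the requirement.

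The conclusion is confined to the stated sample size and power. The trial as expected in the Protocol has ample power for this contrast before loss. How much loss it can bear depends on whether families or individuals drop out. The point should be fixed, but it does not threaten the design.

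**What to change.** Add a dated correction to the Sample size section, or put it in the fuller SAP that the title block announces. Do not present the new figure as what the calculation behind 50 showed. Suggested wording:

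> With SD 2.2 g, a difference of 1.2 g/day (bread alone versus control), a two-sided 5% level, 80% power, ICC 0.33 and equal families of four (design effect 1.99), at least 105 subjects per group are needed: 27 families (108 subjects), or 28 families (112 subjects) with family-level degrees of freedom. This replaces 50.

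If 50 relied on baseline adjustment, state the assumed correlation, the residual ICC and their source instead. In either case, give the power at 450 people in 120 families, with a dropout allowance and the loss pattern assumed (whole families or individuals), and note any allowance for unequal family sizes.

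The cost is wording only. The Protocol says "Data collection is scheduled to be completed during the period 1 January 2018 to August 2018" and the SAP is headed "Date of the document: November 30, 2018", so on the planned schedule recruitment is not affected.

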## **Study Design**

STRIVE (Salt Reduction Intervention) is a single blinded, cluster randomized controlled trial, with children and adults recruited as families and randomly assigned to three parallel intervention arms (A: salt reduced bread; A+B: Salt reduced bread and dietary counseling; C: Bread with standard salt content).

Children and parents are targeted as families, to reflect the real life setting that salt is consumed in and because interventions that target the whole family, rather than single participants, are more effective for achieving dietary goals.

For a period of 14+ weeks, bread (rye bread, wheat bread and buns) will be delivered twice a week to the families, either as bread with gradually reduced salt or with a standard salt content.

All families start with a run-in period of bread with standard salt content, which is gradually lowered in intervention group A and A+B during the first month. The bread intervention begins after the baseline health examination (including urine collection and dietary record) has been completed and runs until data from the endpoint study has been collected.

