### Participants and Recruitment procedures

In January – February 2018 families will be recruited through digital and paper advertisements posted in social media, schools, kindergartens and companies sited in five municipalities (Albertslund, Ballerup, Egedal, Glostrup and Rødvore) in the southwestern part of the Capital Region of Denmark. The area is selected to be close to either Smørum Konditori, the baker that produces the intervention bread, or the research center (Center for Clinical Research and Prevention, Glostrup Hospital), where the health examinations will take place.

Families are defined as minimum one child and one parent living together. Children, who lives fifty percent of their time with each of their divorced parents, will be able to participate if both parents join the study. Participants will be screened to identify participants living with children between 3 and 17 years and with a daily intake of both white and/ or brown bread (> 175 gram of bread/day). Exclusion criteria are: antihypertensive and lipid-lowering treatment, pregnancy, diabetes, coronary heart disease, urine albumin greater than 300 mg/day.

At the end of the baseline health examination families will be systematically randomized by a computer into one of the three groups. In divorced families, both parents (and their families) will follow the randomization of the parent first examined.

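### Does the undefined family ID in the primary model ignore the shared allocation of divorced parents' families?

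*SAP*

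**What the plan says.** The SAP (Statistical analysis) specifies a linear mixed model with "treatment group and baseline sodium excretion as fixed effects, and family ID as random effect". Family ID is the only random effect, and the text does not say how it is assigned.

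The Protocol (Study Design) describes a "cluster randomized controlled trial, with children and adults recruited as families and randomly assigned to three parallel intervention arms". The SAP (Randomization, allocation and concealment) agrees that the unit is the family: "baseline assessments will be conducted before the families will be randomized (1:1:1) to three groups".

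The Protocol (Participants and Recruitment procedures) gives the one definition of a family: "Families are defined as minimum one child and one parent living together". The same section says that children who split their time equally between divorced parents "will be able to participate if both parents join the study", and that in such cases "both parents (and their families) will follow the randomization of the parent first examined". The SAP does not repeat that rule.

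The SAP says twice, in its opening lines and at the end of the statistical section, that a fuller analysis plan is being written.

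**The concern.** In a cluster randomised trial the model has to recognise the unit that was randomised. Under the Protocol's co-residence definition, the two homes of a divorced couple are two families, yet they always fall in the same arm. A programmer who took that definition literally would give them two IDs, and the shared child would fit both.

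The direction of the resulting error is clear. Any positive correlation between linked homes adds to the variance of an arm mean, and a model with separate IDs leaves that part out. The standard error would be too small, the 95% interval too narrow and the p-value too low. The per-protocol model follows the same principles, and the mixed models for the secondary outcomes would probably use the same ID, so the error would carry over.

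**Working it through.** **1. Which unit does the ID denote?** The Protocol uses the word in two ways. Its definition points to the household. Its sentence on shared allocation opens by calling the divorced pair itself a family and then refers to each parent's family. The Study Design section and the SAP's randomisation text both make the family the thing that is randomised. Reading the ID as the randomised unit fits those passages and gives no error. Reading it as the household fits the definition. The text does not decide between them, so the useful question is what the household reading would cost.

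**2. Inputs from the documents.** The Protocol (Methods) expects "450 children and adults divided into 120 families will participate". That is 450/120 = 3.75 people per family and 120/3 = 40 families per arm. The SAP (Sample size) states: "The intra-class correlation within families was assumed to be 0.33 and the average family was assumed to consist of four members". It gives an SD of 2.2 g for salt intake, used here for change as an assumption, and a planned difference of 1.2 g/day. The stated 50 subjects per group does not enter this check. It does not reproduce from those inputs (53 per arm × design effect 1.99 = 106 people, or 27 families of four), which is a separate matter; the expected 40 families per arm exceed 27.

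**3. Assumptions, because the documents give no figures.** The share p of families that are linked is 10 to 20%. That is 12 to 24 families in 6 to 12 pairs, so 114 to 108 independent allocations instead of 120. The number s of shared children per pair is 1 or 2.

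**4. Formulas, with m = 3.75.** In units of SD², the variance of a family mean is v = (1 + (m − 1) × ICC)/m. With ICC 0.33, v = (1 + 2.75 × 0.33)/3.75 = 0.509. If the homes are linked only through shared children, who resemble everyone in both homes at the full ICC, the average cross-home correlation is ρ = s × ICC/m. This is 0.088 for s = 1 and 0.176 for s = 2. Each linked family contributes one extra covariance ρ, so

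true SE / reported SE = √(1 + p × ρ / v).

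The true two-sided error is 2 × (1 − Φ(1.96/ratio)). The reported 95% half-width for an arm difference is 1.96 × 2.2 × √(2 × 0.509/40) = 0.688 g; the true half-width is that figure times the ratio.

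**5. Results under separate IDs.**

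| Case | p | ρ | SE ratio | True error | True half-width |
|---|---|---|---|---|---|
| One shared child | 10% | 0.088 | 1.009 | 5.2% | 0.694 g |
| One shared child | 20% | 0.088 | 1.017 | 5.4% | 0.700 g |
| Two shared children | 10% | 0.176 | 1.017 | 5.4% | 0.700 g |
| Two shared children | 20% | 0.176 | 1.034 | 5.8% | 0.711 g |
| Homes as alike as one family | 20% | 0.330 | 1.063 | 6.5% | 0.731 g |

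**6. Weaker links.** A child who spends half the time in each home need not resemble both homes fully. Halving ρ gives ratios of 1.004 to 1.017. The ICC of baseline-adjusted change may also differ from 0.33. At 0.10, v = (1 + 2.75 × 0.10)/3.75 = 0.340 and the ratios are 1.004 to 1.016. With both (ρ = 0.013 to 0.027), they are 1.002 to 1.008, and the true error is at most about 5.2%.

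**7. Check by simulation.** A t-test on family means under the null, 40 families per arm and ICC 0.33, rejected in 4.98% of 200,000 replicates with no linked families. It rejected in 5.2 to 5.8% over the first four rows of the table and in 6.56% in the last row. The formula and the simulation agree.

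**8. Effect on a conclusion.** If the observed difference were 1.2 g/day, the lower confidence limit would be 1.2 − 0.688 = 0.51 g as reported, and 1.2 − 0.731 = 0.47 g in the last row. The reading is the same.

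**The case for a change.** The best argument for acting is that the Protocol's only definition of a family is by household, that nothing states the ID is the allocation unit, and that one sentence and one variable would settle it from information already held at screening and randomisation. The promised fuller plan does not say it will cover this, and the primary model is already written down.

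The gap in the text is real, and the direction of any bias is not in doubt. The last row of the table is not a bound either: with 30% of families linked, two homes as alike as one, and four people per family, the SE ratio reaches 1.095.

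The rest is weaker. No error is shown, because the result depends on three conditions that the documents leave open. The 10 to 20% share has no source in them. The shared-child rows are generous: each child gives a single weekend-day urine collection (Protocol, Urine Collection), which will tend to reflect the home the child is in that day. The obvious remedy, one shared ID as the sole random effect, is not exact: it treats people in two homes as being as alike as people in one. The matching model would nest household within allocation unit, and with perhaps 6 to 12 linked pairs over three arms the extra variance component would be poorly estimated.

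**Conclusion.** The concern identifies a missing definition, not a flaw in the primary analysis. The standard reading of a cluster effect in a cluster randomised trial is the randomised unit, which both documents call the family; under that reading nothing is wrong. Under the household reading, the true standard error would exceed the reported one by about 0 to 3% for plausible linkage, and by about 6% in an assumed high case. True two-sided error would be 5.0 to 5.8%, or 6.5% in the high case. These sizes rest on an assumed share of linked families, an assumed route of correlation, the SAP's ICC applied to change, and the SAP's intake SD applied to change. The effect is zero if no linked families enrol, if they share an ID, or if the homes are uncorrelated. No conclusion at the planned 1.2 g/day difference would alter. How to code the ID for an uncommon family structure is a detail that analysts settle when they build the data set, under a SAP that calls itself provisional. No change to the plan is needed.
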